2.15.4 Challenges to identifying the legally acceptable representative for consent	
process	24
2.15.5 Failure of long read metagenomic sequencing	25
2.15.6 Reliable antibiotic consumption data	25
2.15.7 Global pandemic/Local epidemic	26
2.16 Future use of stored samples	26
2.17 Budget and finance	26
2.17.1 Budget justification	26

Version 5.0 21/05/2025

Executive Summary

Study type: This is a multi-site, extended observational case-control study with a preliminary cohort component.

Problem: Based on modelling, Sub-Saharan Africa is the region most affected by death due to antimicrobial resistance (AMR), but there is little AMR data from the region. Pneumonia remains a leading cause of death in children under 5 years old worldwide. To change this, we must understand how antibiotic selective pressure and healthcare exposure impacts AMR development and how AMR influences health outcomes in resource limited settings. The nasopharynx is a reservoir of organisms that cause pneumonia and their associated AMR. Metagenomic deep-sequencing enables identification of the nasopharyngeal resistome (NPR), all the genetic determinants of AMR within the nasopharyngeal bacterial niche. No study has examined whether human resistome composition is associated with health outcomes.

Objectives: Our study aims to answer the following research question; does hospital admission and antibiotic treatment for pneumonia generate a persistent hospital-acquired nasopharyngeal resistome in Malawian children, and is this associated with adverse health

 To measure how the diversity and relative abundance of the nasopharyngeal resistome of children hospitalised with pneumonia differs from the nasopharyngeal resistome of healthy children in the community.

outcomes in a resource limited setting? The primary objectives of this study are:

- To measure how the diversity and relative abundance of the nasopharyngeal resistome of children hospitalised with pneumonia differs from the nasopharyngeal resistome of children with pneumonia treated with antibiotics in the community.
- To investigate whether there is measurable persistence of a hospital-acquired nasopharyngeal resistome post-discharge, and whether this is associated with adverse health outcomes, including recurrent hospitalisation.

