1.1 Rationale

There is limited data on NPR evolution under antibiotic selective pressure and following exposure to a hospital environment. No study has examined whether human resistome composition (ARG abundance and diversity) is associated with health outcomes.

Malawi has limited healthcare resources and a high incidence of pneumonia in children aged 12-24 months [17]. Our study will describe the impact of antibiotic selective pressure and exposure to the hospital environment on the NPR of Malawian children with pneumonia. The study will investigate the hypothesis that among these children a hospital-acquired NPR is associated with adverse health outcomes following discharge, by examining whether NPR composition is associated with hospital readmission.

We have chosen to focus on hospital re-admission as an adverse outcome related to AMR in pneumonia, because severe pneumonia requiring hospitalisation is more commonly bacterial in aetiology [6]; thus, re-hospitalisation is more likely to reflect the impact of AMR in bacterial pneumonia. Alongside the World Health Organisation (WHO) markers of severity in pneumonia, a range of adverse health outcomes of AMR in bacterial pneumonia will be recorded, including additional episodes of pneumonia, additional courses of antibiotics and their duration, and mortality outcomes.

Antibiotic use prior to seeking healthcare input is common in Malawi; 70% of patients report self-administration of antibiotics in this setting [18], which correlates with recent unpublished evidence of antibiotic activity detected in urine assays in hospitalised children.

Disentangling the impact of antibiotics and hospital admission on the resistome could inform public health interventions, including prescribing practices and hospital admission policies.

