2.0 Methodology

2.1 Study design

This is a multi-site, extended case-control study with a preliminary cohort component to assess the evolution of the NPR under selective pressure of antibiotic use and hospital admission for pneumonia in children aged 12-24 months in Malawi. The study will be led by the PhD student, [name], as a PhD fellowship.

NP Resistome Study

Version 5.0 21/05/2025

Page 10 of 30

In the preliminary cohort component, healthy children in the community will have a NPS collected at the first study visit, to determine the baseline community resistome through metagenomic sequencing (see Figure 1).

To assess the impact of oral antibiotics on the NPR, children presenting with pneumonia to community healthcare clinics, Ndirande and Gateway Primary Care Centre (GPCC), will have a NPS collected at the first study visit and 3-months post-recruitment, to determine the antibiotic-exposed resistome through metagenomic sequencing (see Figure 1).

To understand the impact of broad-spectrum intravenous antibiotics and exposure to a hospital environment on the NPR, children hospitalised with pneumonia (without any hospital admission 6 months prior) to Queen Elizabeth Central Hospital (QECH) will have a NPS collected at the first study visit, discharge and 3-months post-recruitment to determine a hospital-acquired resistome through metagenomic sequencing (see Figure 1).

[figure not shown]

Figure 1. Preliminary cohort component of the study. The yellow diamonds represent the key samples groups for NPR comparison.

The case-control component of the study will examine whether a hospital acquired NPR is associated with adverse health outcomes, specifically re-admission to hospital with pneumonia. Children hospitalised to QECH with pneumonia (without admission 6 months prior), who are not re-admitted within 3 months will form the control group (see Figure 2); these participants will have a NPS will be collected at the first study visit (within 24 hours of admission to hospital), discharge from hospital and 3-months post-recruitment to assess for a hospital-acquired resistome. Those hospitalised within the preceding 6 months will be

NP Resistome Study

Version 5.0 21/05/2025

Page 11 of 30

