Age, gender, co-morbidities, mid-upper arm circumference, pneumococcal vaccination status, antibiotics received 7 days prior to recruitment, haemoglobin level and malaria screening results will be recorded for all participants at recruitment; exposure to tobacco smoke from a household contact and whether the participant was breastfed in their first 3 months of life will also be recorded, as these are independently associated with pneumonia requiring hospitalisation in high-income settings [21]. Mode of childbirth (vaginal versus caesarean section) will also be recorded, as this influences early NPM development, and may be associated with childhood respiratory health [22]. To assess for acquisition of MGEs from the hospital environment, we will record data on duration of hospitalization and incidence of shared bed-spaces for hospitalised study participants, including number of occupants and number of days in a shared bed-space. Shared hospital bed-spaces will be sampled using a swab for metagenomic sequencing. Groups undergoing repeat NPS at 3 months will have health outcomes (including mortality), healthcare interactions (including healthcare facility and hospital attendance/admission) and antibiotic exposure recorded.

Groups being admitted to hospital will have WHO markers of severity in pneumonia recorded, including presence of the following at the time of admission: central cyanosis, oxygen saturations less than 90%, inability to feed, vomiting, convulsions, lethargy and impaired consciousness. To assess for potential influence of healthcare seeking behaviour on hospital re-admission, groups presenting to healthcare clinics and/or hospitals with pneumonia will have the educational level of the parents recorded, and the distance travelled to the healthcare clinic.

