2.4 Study period

This study will be conducted over a three-year period as a PhD fellowship, with participant recruitment over an 18-month period; see Figure 3. Due to the budget, our study team will not have the capacity to recruit in the community and hospital concurrently; community participants will be recruited prior to hospital participants.

We have chosen a 3-month follow up timepoint, to allow the resistome to return to a post-antibiotic baseline; a previous study demonstrated microbiome recovery within 3 months of infective-asthma exacerbation [23].

Importantly, there is evidence of seasonal variation in composition of the NPM and NPR [24]. Unfortunately, our study team size is restricted by budgetary constraints, therefore we are unable to recruit in the community and hospital simultaneously. We plan to conduct most of the community patient recruitment intensively within a 6-month period, before starting hospital recruitment. To restrict potential confounding due to seasonal effect, we plan to return to the community on an infrequent basis (approximately 3-4 weekly) for healthy community sampling over the following 6 months to ensure a baseline healthy resistome has been sampled across all seasons.

NP Resistome Study

Version 5.0 21/05/2025

Page 14 of 30

	December 2024 - February 2025	March - May 2025	June - August 2025	September - November 2025	December 2025 - February 2026	March - May 2026	June - August 2026	September - November 2026	December 2026 - February 2027	March - May 2027	June - August 2027
Set up study in-country											
Recruitment and data											
collection from COMMUNITY cohort											
Recruitment and data											
collection from											
HOSPITAL cohort DNA extraction and											
sequencing											
Bioinformatic pipeline											
optimisation											
Statistical analysis and thesis preparation											

Figure 3. Study timeline

Samples collected from study participants will be stored for 5 years after the conclusion of the study at Malawi Liverpool Wellcome program. The study will be completed within 18 months of the start of recruitment, or when the recruitment targets have been achieved and all samples collected (if this occurs in a time frame shorter than 18 months). Upon study completion, the Sponsor (LSTM), RECs and MLW will be notified; a report of the study findings will be submitted to COMREC, Blantyre district health office and LSTM.

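### Persistence is known only from the 3-month swab, and no outcome recording after that visit is described, so objective 3 cannot show that persistence precedes harm

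*Protocol*

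**What the plan says.** The Executive Summary gives the third primary objective as "To investigate whether there is measurable persistence of a hospital-acquired nasopharyngeal resistome post-discharge, and whether this is associated with adverse health outcomes, including recurrent hospitalisation"; section 1.3.2 repeats it. The exposure in that sentence is persistence after discharge.

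For children hospitalised with pneumonia, section 2.1 plans an "NPS collected at the first study visit, discharge and 3-months post-recruitment to determine a hospital-acquired resistome". Section 2.4 names a single follow-up point and gives its reason: "We have chosen a 3-month follow up timepoint, to allow the resistome to return to a post-antibiotic baseline".

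On outcomes, section 1.1 says that a range will be recorded, "including additional episodes of pneumonia, additional courses of antibiotics and their duration, and mortality outcomes". Section 2.1 ties the recording to the swab schedule: "Groups undergoing repeat NPS at 3 months will have health outcomes (including mortality), healthcare interactions" and antibiotic exposure recorded.

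Section 2.1 places the re-admission question in a case-control component. Cases are children admitted within 3 months of an earlier pneumonia admission, swabbed once, within 24 hours of the new admission. For controls, hospitalised children "who are not re-admitted within 3 months will form the control group". Section 2.9.2 relates re-hospitalisation to resistome composition by conditional logistic regression; the text does not say which of the controls' three swabs is used.

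**The concern.** For an exposure to be read as leading to an outcome, it must be measured before the outcome, or at least not be changed by it. Here the outcome window closes at the visit where persistence is first observed.

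The outcomes can also alter the exposure. Section 1.2 hypothesises that antibiotics and hospital exposure change the resistome. A further antibiotic course or a new admission between discharge and 3 months would then, on the protocol's own reasoning, leave its mark on the 3-month swab. Genes acquired again would look like genes retained. Section 2.4 justifies 3 months as time for recovery from antibiotics, and a child treated again in the interval has not had that time.

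At stake is the outcome half of a primary objective. An association could appear even if the hospital-acquired resistome were harmless, and section 1.1 says the work could inform prescribing practices and hospital admission policies.

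**Working it through.** The point rests on the order of measurements, so the schedule comes first. The counts only show how much information a re-ordered analysis would have.

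**Order of measurements, hospital cohort (sections 2.1 and 2.4)**

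| Time | Swab | What it can show | Outcomes recorded after it |
|---|---|---|---|
| Admission (within 24 hours) | yes | starting resistome | admission to 3 months |
| Discharge | yes | genes acquired in hospital | discharge to 3 months |
| 3 months post-recruitment | yes | persistence | none described |

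Outcome time after the persistence measurement = 3 months − 3 months = 0. That recording ends at 3 months is inferred from the single follow-up point and the absence of any later contact; the protocol does not say so outright.

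**Order of measurements, case-control component (section 2.1)**

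- Cases: one swab, taken at the re-admission. The outcome has already occurred, and antibiotics may have been taken before admission.
- Controls: three swabs, but by definition no re-admission within 3 months.
- Neither group supplies a persistence measurement followed by a re-admission.

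**The protocol's own figures (sections 2.5 and 2.15.1)**

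1. n per group = 2(1.960 + 1.282)² / 0.505² = 82.4, rounded up to 83. This reproduces the stated 83.
2. Followed groups: 83 × 1.10 = 91.3, rounded up to 92, as stated. (83 / 0.90 would give 93; the difference is immaterial here.) 92 × 0.90 = 82.8, about 83 retained.
3. Total: 83 + 92 + 92 + 83 = 350, as stated.
4. Re-admissions in the feasibility section: 500 × 0.18 = 90, as stated.

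**Expected re-admissions in the hospital cohort by 3 months**

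Inputs: 92 children (section 2.5) and 18% over 6 months (section 2.15.1, borrowed from severe anaemia).

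- Linear: 0.18 / 2 = 0.09; 92 × 0.09 = 8.3.
- Constant hazard: 1 − √(1 − 0.18) = 0.0945; 92 × 0.0945 = 8.7.
- Range, constant hazard: 2.3 if the 6-month rate were 5%, and 12.3 if it were 25%. Both rates are assumptions.

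Under the schedule described, all of these would fall before the 3-month swab and none after it. The interval from discharge to 3 months post-recruitment is somewhat shorter than 3 months, so these counts lean high.

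**The case against.** The strongest reply is that the protocol never states an analysis of outcomes on the 3-month swab. Section 2.1 gives the outcome question, specifically re-admission, to the case-control component, and section 2.9.2 contains the only outcome model. Section 1.1 says merely that the wider outcomes will be recorded. Section 2.9 is a summary, and a detailed SAP, not shown here, could choose the swab and define persistence. The objective also asks only about association.

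Much of that stands, and it rules out several stronger readings that a reader might infer:

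- *That the plan commits to regressing outcomes on the 3-month swab.* It does not. The objective links outcomes to persistence, and only that swab can measure persistence, but no such model is written.
- *That the 8 or so re-admitted children distort the case-control comparison.* They are excluded from the controls by definition. The count describes the cohort only.
- *That the discharge swab is ignored.* Section 2.1 lists it, with the other two, for assessing a hospital-acquired resistome, and section 1.2 refers to the resistome at discharge. Figures 1, 2 and 4, which may assign swabs to comparisons, are not available.
- *That 70% self-medication measures how many 3-month swabs are affected.* Section 2.15.6 attributes it to adults in rural Malawi, and it is not a 3-month rate in children.

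What the reply does not remove is the timing. An SAP can choose among planned swabs, but it cannot place recorded outcomes after the last visit. Nor does moving the question to the case-control component help, since the case swab is taken at the outcome.

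**Conclusion.** The concern holds for the outcome half of objective 3. With the measurements described, persistence cannot be related to any later outcome. An association in the hospital cohort between the 3-month resistome and interim pneumonia, antibiotic courses or admissions would be retrospective and open to reverse causation. Children who die before 3 months cannot be classified for persistence, although mortality is a named outcome. The case-control component does not repair this.

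In size, recorded outcome time after the persistence swab is zero. This assumes that no contact follows the 3-month visit. The figure of about 8 re-admissions among 92 (8.3 to 8.7) is illustrative: it uses a rate from severe anaemia, a condition excluded from this group, and section 2.15.1 says that no pneumonia re-admission data exist for the region. The timing argument does not depend on it.

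A reader might infer that objective 3 as a whole, or the study, fails. The documents do not support that. Whether persistence is measurable can still be described, and objectives 1 and 2 and the sample size do not depend on this outcome timing.

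**What to change.** 1. For the cohort part of objective 3, name the discharge swab, or the change from admission to discharge, as the exposure. Relate it to outcomes from discharge to 3 months in all enrolled hospital children, including those re-admitted or who die. A child who dies before discharge has no discharge swab and should be counted and reported as such.
2. Define persistence as genes acquired between admission and discharge and still present at 3 months. Report it separately, split by whether there was an interim admission or antibiotic course.
3. State that associations between the 3-month resistome and earlier outcomes are not evidence that persistence leads to harm.
4. State which control swab is compared with the case swab, and that the case swab is taken at the outcome.

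The cost is wording in the protocol and SAP: the swabs and the interim admission and antibiotic data are already planned. The price is precision. With about 8 re-admissions expected on the borrowed rate, the outcome estimate should be given with its interval and described as imprecise.

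Relating persistence itself to later outcomes would need contact after the 3-month visit. As an illustration, a further 3 months in the 83 children retained would give 83 × 0.09 = 7.5 to 83 × 0.0945 = 7.8 re-admissions at the same rate. That would be new fieldwork for a similarly small number of events.

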1.3.2 Primary Objectives

- To measure how the diversity and relative abundance of the nasopharyngeal resistome of children hospitalised with pneumonia differs from the nasopharyngeal resistome of healthy children in the community.
- To measure how the diversity and relative abundance of the nasopharyngeal resistome of children hospitalised with pneumonia differs from the nasopharyngeal resistome of children with pneumonia treated with antibiotics in the community.
- Investigate whether there is measurable persistence of a hospital-acquired nasopharyngeal
 resistome post-discharge, and whether this is associated with adverse health outcomes,
 including recurrent hospitalisation.

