2.7.3.3 Inclusion criteria for children with pneumonia in the community

- Child aged between 12-24 months.
- Presence of all of the following symptoms: fever, cough, difficulty in breathing and fast breathing.
- Participant has been prescribed antibiotics for treatment of a lower respiratory tract infection on this presentation.

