2.9.1 Primary analysis

Participants will be gender-matched across groups. To establish differences in NPR composition the mean NPR diversity in a sample (measured using the Shannon index), mean relative abundance of all ARGs in a sample and mean relative abundance of specific ARGs in a sample will be compared between study groups using unadjusted t-tests, as summarised in Figure 4. Statistical analysis will be performed in R. Results will be presented in tables and illustrative heatmaps.

[figure not shown]

Figure 4. Plan for statistical analysis of NPR composition.

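### WHO severity markers are recorded only in admitted children, so the community-pneumonia comparator of primary objective 2 has no acute severity measure

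*Protocol*

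**What the plan says.** The second primary objective (Protocol 1.3.2) asks how the resistome of children hospitalised with pneumonia "differs from the nasopharyngeal resistome of children with pneumonia treated with antibiotics in the community". Section 2.1 gives the purpose of the hospitalised group: "To understand the impact of broad-spectrum intravenous antibiotics and exposure to a hospital environment on the NPR".

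On data collection, section 2.1 sets three scopes:

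- **All participants.** The list includes "antibiotics received 7 days prior to recruitment, haemoglobin level and malaria screening results will be recorded for all participants at recruitment", together with age, gender, co-morbidities, arm circumference, vaccination status and some early-life and household exposures. None of these measures how severe the acute pneumonia is.
- **Admitted groups only.** "Groups being admitted to hospital will have WHO markers of severity in pneumonia recorded, including presence of the following at the time of admission". Seven signs follow: central cyanosis, saturation below 90%, inability to feed, vomiting, convulsions, lethargy and impaired consciousness.
- **Clinic and hospital pneumonia groups.** "groups presenting to healthcare clinics and/or hospitals with pneumonia will have the educational level of the parents recorded, and the distance travelled". This wider scope covers only those two items.

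Section 1.1 mentions the WHO markers without naming groups and does not extend them to clinic children.

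The community-pneumonia group enters on "Presence of all of the following symptoms: fever, cough, difficulty in breathing and fast breathing" plus an antibiotic prescription (2.7.3.3). The hospitalised group has the same criteria (2.7.3.5), and the exclusions in 2.7.3.4 and 2.7.3.6 also match. In section 2.9.1 the resistome measures "will be compared between study groups using unadjusted t-tests, as summarised in Figure 4", with gender as the only matching factor. Severity of pneumonia is listed as a potential confounder in section 2.9.2, but only in the model for re-hospitalisation.

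**The concern.** Because the entry criteria are the same, eligibility does not equalise severity between the two pneumonia groups; admission separates them, and admission plausibly follows severity. The protocol itself gives a reason why severity could also relate to the resistome: in section 1.1 it states that "severe pneumonia requiring hospitalisation is more commonly bacterial in aetiology". A group difference could therefore come partly from sicker, more often bacterial disease and still be read as an effect of the hospital environment or of intravenous antibiotics. Section 1.1 hopes that separating those influences could inform prescribing and admission policy, so the attribution matters.

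The gap is one of data, not of analysis detail. A statistical analysis plan could add adjustment, but not for a variable that was never collected in the comparator. Under section 2.4 most community recruitment is finished before hospital recruitment starts, so the loss is fixed early.

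**Working it through.** **1. Is the restriction explicit?** The sentence on severity names the admitted groups. The next sentence, on education and distance, names clinic and hospital groups together. The authors widened the scope where they wanted it, so the narrower scope for severity is what the text says. Where severity is planned as a covariate (2.9.2), cases and controls are all admitted children, so the data exist there. In the contrast for objective 2 they exist on one side only.

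**2. The plan's own figure.** Inputs from section 2.5: Δ = 0.505, two-sided 5%, 90% power.

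n = 2(1.960 + 1.282)² / 0.505² = 82.4, rounded up to 83 per group.

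This matches the stated 83 (power 90.2%). The sample size is not in question; 83 per group is used below as the planned evaluable number.

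**3. Size of the possible bias.** The documents give no input for this, so both inputs are assumptions:

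- d = difference between the groups in the proportion with severe disease
- g = shift in the resistome measure in a severe child, in SD

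With no true hospital effect, spurious difference b = d × g. The standard error is √(2/83) = 0.155 SD. The two-sided 5% test rejects with probability Φ(b/0.155 − 1.96) + Φ(−b/0.155 − 1.96).

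Middle case: d = 0.40 and g = 0.5 give b = 0.20 SD, which is 40% of the design effect (0.20/0.505). Then b/SE = 1.29, and the test rejects in about 25% of studies.

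| d | g = 0.2 SD | g = 0.5 SD | g = 0.8 SD |
|---|---|---|---|
| 20 points | 0.04 SD, 6% | 0.10 SD, 10% | 0.16 SD, 18% |
| 40 points | 0.08 SD, 8% | 0.20 SD, 25% | 0.32 SD, 54% |
| 60 points | 0.12 SD, 12% | 0.30 SD, 49% | 0.48 SD, 87% |
| 80 points | 0.16 SD, 18% | 0.40 SD, 73% | 0.64 SD, 98% |

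**4. What adjustment would cost in precision.** Take a binary severity covariate with assumed prevalence p₁ (hospital) and p₀ (clinic), and mean p̄. Then R² = 0.25(p₁ − p₀)² / [p̄(1 − p̄)], and the variance of the adjusted difference rises by 1/(1 − R²). At 83 per group, power for 0.505 becomes:

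- 40% v 20%: inflation 1.05, power 89%
- 60% v 20%: inflation 1.20, power 84%
- 70% v 10%: inflation 1.60, power 73%
- 90% v 10%: inflation 2.78, power 50%

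For the restricted comparison, suppose half or a quarter of 83 hospital children are marker-free, against 83 clinic children. The standard errors are √(1/83 + 1/41.5) = 0.190 and √(1/83 + 1/20.75) = 0.245, and power for 0.505 is about 76% and 54%.

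The adjusted result is therefore best treated as a supportive estimate with its interval, not as a second test.

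**The case against.** - **Other data help.** Every admitted child has the markers, so the hospital group can be restricted to marker-free children and the severity–resistome association can be estimated within it. Hospital children are swabbed within 24 hours of admission and again at discharge, and the within-child change holds admission severity fixed. A reader might infer that no later analysis could do anything about severity; that goes too far. What stands is that none of this supplies severity in the comparator. The within-child change is also a different contrast from objective 2: it still mixes environment with intravenous treatment, and clinic children have swabs only at the first visit and at 3 months.
- **The objective is descriptive.** It asks how the groups differ, and an unadjusted comparison answers that. This is fair as to the objective's wording. But sections 1.1 and 2.1 read the hospital group in terms of impact, and that reading needs severity.
- **The causal path is not stated by the protocol.** A reader might infer that the protocol itself says severity raises resistance-gene abundance. It does not. Section 1.2 is a hypothesis about abundance at discharge and does not mention severity. The link from severity to the resistome is plausible, not documented.
- **Severity is not the only difference.** Recruitment sites differ (2.2), and so does calendar period: the later community visits are for healthy children only (2.4). Recording severity would not by itself isolate hospital exposure.
- **Clinic children may have no danger signs.** The eligibility criteria do not exclude children with them. Recording would settle the question, although adjustment would be weak if overlap is thin.

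Figure 4 is not shown, so the swabs compared in the t-tests cannot be checked. The text does fix the tests as unadjusted.

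**Conclusion.** The point holds as a measurement gap in a primary contrast. The community-pneumonia group has no acute severity measure, so a severity imbalance in objective 2 cannot be described, or adjusted for directly, in the comparator. How much this biases the result is unknown. The middle case gives 0.20 SD and about 25% rejection with no hospital effect, and the range of 6% to 98% shows how far the answer depends on inputs that the protocol does not give.

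A reader might infer a rejection rate near 90% by entering 0.5 SD directly as the difference in group means. That would treat every admitted child as severe and no clinic child as severe, which nothing in the documents supports. It also nearly repeats the design power, since 0.5 is close to 0.505.

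This is a worthwhile and inexpensive improvement. The study can run without it, but objective 2 would then give weak support to any statement about hospital exposure.

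**What to change.** **Section 2.1.** Widen the severity sentence from the admitted groups to 'All groups with pneumonia', with the markers recorded at admission or at the first clinic visit.

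**Section 2.9, for objective 2.** Add:

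1. a table of marker prevalence by group;
2. a supportive comparison, either adjusted for severity or restricted to children without markers, using the same marker set in both groups. If oxygen saturation is not available in both, leave it out of the definition in both; otherwise being marker-free would mean seven signs in one group and six in the other;
3. estimates with confidence intervals;
4. a statement that the unadjusted difference alone is not attributed to hospital exposure, and that site and calendar period remain as differences.

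Do not add a rule that depends on whether a difference appears only in children with markers. It would read a non-significant result in a smaller subset as absence of effect.

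**Cost.** Up to seven extra CRF items, mostly bedside observation, at a visit that already takes place, and a less precise supportive estimate where severity overlap is thin. Eligibility, treatment and sample size do not change.
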